1.1 STUDY OBJECTIVES AND ENDPOINTS

Table 1: Objectives and endpoints

Objectives	Endpoints
Primary	
To assess the long-term safety and tolerability of treatment with efgartigimod PH20 SC in participants with BP	
 • Incidence and severity of treatment-emergent AEs, SAEs, and AESIs • Rate of treatment discontinuation because of safety concerns
Secondary	
To assess the long-term efficacy and durability of response with efgartigimod PH20 SC treatment in participants with BP	
 • Proportions of participants achieving^a: 
 ○ CR while off OCS for ≥ 8 weeks ○ CR or PR while off OCS for ≥ 8 weeks ○ CR while on minimal OCS therapy for ≥ 8 weeks. (Minimal OCS therapy is defined as ≤ 0.10 mg/kg/day of prednisone [or an equivalent dose of another OCS]) ○ CR while off both OCS and efgartigimod PH20 SC for ≥ 8 weeks^b ○ CR or PR while off both OCS and efgartigimod PH20 SC for ≥ 8 weeks^b • Duration of sustained remission • Proportion of participants who relapse • Time to relapse • Incidence and severity of relapse • BPDAI activity scores, IGA-BP scores, and itch NRS over time • Rate of treatment failure

	Statistical Analysis Plan	
ARGX-113-2010	Final analysis	Final 1.0 of 29APR2025

Additional secondary	
To evaluate the impact of efgartigimod PH20 SC treatment in reducing long-term glucocorticoid-associated toxicity in participants with BP	
 GTI-related scores, including the GTI-AIS, GTI-CWS, and GTI-SL over time
To evaluate the impact of efgartigimod PH20 SC treatment on QoL in participants with BP	
 EQ-5D-5L, DLQI, and ABQOL scores over time
To evaluate the PD and immunogenicity of efgartigimod PH20 SC in participants with BP	
 Percent change from baseline over time for anti-BP180 and anti-BP230 antibody levels Incidence and prevalence of ADA against efgartigimod (serum levels)
Exploratory	
[REDACTED]	
 [REDACTED]

- ^a These endpoint criteria can only be met when participants are off rescue therapy.
- ^b The endpoint applies only to participants who have stopped receiving efgartigimod PH20 SC before protocol amendment 2 is effective.

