2.2 PHASES, PERIODS AND TIME POINTS

2.2.1 *Analysis phases, periods and subperiods*

All assessments and events will be allocated to analysis phases, periods and subperiods as defined in below table.

Table 2: Analysis phase, period and subperiod definition

Phase	Period/Subperiod	Start	End
For participants who don't receive the first IMP administration at the ARGX-113-2010 baseline visit^a, the first phase will be the observation phase.			
For participants who receive the first IMP administration at the ARGX-113-2010 baseline visit^a, the first phase will be the treatment phase.			
Observation		Date of baseline visit in ARGX-113-2010, with 00:00 added as time part	
For participants with a subsequent treatment period:
 
First IMP administration date/time – 1 minute.
 
For other participants:
 
Date of week 48 or EDV visit^c, with 23:59 added as time part.
 
For participants who don't have a week 48 or EDV visit: date of last contact, with 23:59 added as time part.

	Statistical Analysis Plan	
ARGX-113-2010	Final analysis	Final 1.0 of 29APR2025

Phase	Period/Subperiod	Start	End
Treatment	Treatment period 1/ On IMP treatment	
For participants with first IMP administration at the baseline visit:
 
Date of baseline visit in ARGX-113-2010, with 00:00 added as time part.
 
For participants with a previous observation phase and who initiate treatment:
 
First IMP administration date/time
	
For participants with a subsequent Off IMP subperiod:
 
Last IMP administration date/time in treatment period 1.
 
For other participants:
 
Date of week 48 or EDV visit^c, with 23:59 added as time part.
 
For participants who don't have a week 48 or EDV visit: date of last contact, with 23:59 added as time part.

	Treatment period 1/ Off IMP treatment	Last IMP administration date/time in treatment period 1 + 1 minute	
For participants with a subsequent treatment period:
 
First IMP administration date/time in next treatment period – 1 minute.
 
For other participants:
 
Date of week 48 or EDV visit^c, with 23:59 added as time part.
 
For participants who don't have a week 48 or EDV visit: date of last contact, with 23:59 added as time part.

Treatment period 2 is applicable for participants who re-initiate IMP administration after a previous Off IMP subperiod^b.			

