Treatment	Treatment period 2/ On IMP treatment	First IMP administration date/time in treatment period 2	
For participants with a subsequent Off IMP subperiod:
 
Last IMP administration date/time in treatment period 2.
 
For other participants:
 
Date of week 48 or EDV visit^c, with 23:59 added as time part.
 
For participants who don't have a week 48 or EDV visit: date of last contact, with 23:59 added as time part.

	Treatment period 2/ Off IMP treatment	Last IMP administration date/time in treatment period 2 + 1 minute	
Date of week 48 or EDV visit^c, with 23:59 added as time part.
 
For participants who don't have a week 48 or EDV visit: date of last contact, with 23:59 added as time part.

	Statistical Analysis Plan	
ARGX-113-2010	Final analysis	Final 1.0 of 29APR2025

Phase	Period/Subperiod	Start	End
Follow-up		End of previous phase + 1 minute	Date of last contact, with 23:59 added as time part.

- ^a First IMP administration is considered to occur on the ARGX-113-2010 baseline visit if the date of first IMP administration equals the scheduled baseline visit start date (SVSTDTC) or end date (SVENDTC), or if the first IMP administration occurs on an unscheduled baseline visit. In either case, the first phase starts with SVSTDTC of the first scheduled or unscheduled baseline visit.
- ^b A new treatment period is considered for participants with relapse after achieving CR or PR while being off concurrent BP therapy for ≥ 8 weeks before protocol amendment 2 was effective, or at the investigator's discretion after protocol amendment 2 was effective. For programming purposes, a new treatment period will be considered if a participant has a gap of at least 4 weeks (28 days) between two consecutive IMP administrations that cannot be attributed to missed visits or non-efficacy related reasons documented on the study drug administration eCRF form.
- ^c SVENDTC of the last scheduled or unscheduled week 48 or early discontinuation visit will be used.

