ARGX-113-2010	Final analysis	Final 1.0 of 29APR2025

Else, the participant will be considered a CR/PROff non-responder. Participants who already have the disease status CR or PR at day 1 of the treatment period or who are off OCS therapy at day 1 of the treatment period or who receive rescue therapy at day 1 of the treatment period, will be considered non-evaluable for this endpoint and will be excluded from this analysis for the corresponding treatment period.

- 3) Participants achieving CR while on minimal OCS therapy for ≥ 8 weeks (CRmin). A participant will be considered a CRmin responder if the following criteria are met simultaneously for ≥ 8 weeks (56 days):
- The participant's reported disease status is CR
 - The participant receives ≤ 0.10 mg/kg/day of prednisone (or an equivalent dose of another OCS)
 - The participant does not receive any rescue therapy (as indicated by the investigator on the eCRF). OCS used as rescue therapy will not be considered as rescue therapy if the above criterium of minimal OCS therapy is still met.

Else, the participant will be considered a CRmin non-responder. Participants who already have the disease status CR at day 1 of the treatment period or who are on minimal (≤ 0.10 mg/kg/day) OCS therapy at day 1 of the treatment period or who receive rescue therapy at day 1 of the treatment period, will be considered non-evaluable for this endpoint and will be excluded from this analysis for the corresponding treatment period.

- 4) Participants with treatment failure.

The following endpoints will be derived **for each treatment period separately and additionally for the observation phase:**

- 5) Participants achieving CR while off both OCS and efgartigimod PH20 SC for ≥ 8 weeks (CROff without IMP). A participant will be considered a responder for CROff without IMP if the following criteria are met simultaneously for ≥ 8 weeks (56 days):
- The participant's reported disease status is CR
 - The participant is off OCS therapy
 - The participant is off IMP
 - The participant does not receive any rescue therapy (as indicated by the investigator on the eCRF)

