Else, the participant will be considered a non-responder for CROff without IMP. Participants who enter the ARGX-113-2010 study under protocol version 3 (26 April 2024) or 4 (02 May 2024) will be considered non-evaluable for this endpoint. Furthermore, participants who were randomized to the placebo arm in the ARGX-113-2009 study and who enter the ARGX-113-2010 study in the observation phase, will be considered non-evaluable for this endpoint in the observation phase.

- 6) Participants achieving CR or PR while off both OCS and efgartigimod PH20 SC for ≥ 8 weeks (CR/PROff without IMP). A participant will be considered a

	Statistical Analysis Plan	
ARGX-113-2010	Final analysis	Final 1.0 of 29APR2025

responder for CR/PROff without IMP if the following criteria are met simultaneously for ≥ 8 weeks (56 days):

- The participant's reported disease status is CR or PR (continuously or alternately)
- The participant is off OCS therapy
- The participant is off IMP
- The participant does not receive any rescue therapy (as indicated by the investigator on the eCRF)

Else, the participant will be considered a non-responder for CR/PROff without IMP. A participant will be considered non-evaluable for this endpoint using the same rules as for CROff without IMP.

- 7) Duration of sustained remission will be calculated for participants achieving CR while off both OCS and efgartigimod PH20 SC for ≥ 8 weeks (i.e., responders for CROff without IMP) within a treatment period.
 - Start date of sustained remission is 1 week (7 days) after the last IMP administration in the treatment period
 - End date of sustained remission is:
 - the start date of first relapse after achieving CROff without IMP
 - the start date of a (next) treatment period
 - the start date of OCS therapy after achieving CROff without IMP
 - the start date of a rescue therapy after achieving CROff without IMP
 whichever comes first. If none of the above occurs, the participant will be censored at the end date of the study (end date of last phase).
 - Duration of sustained remission (in days) = end date - start date + 1
- 8) Relapse will be evaluated for participants having or achieving CDA, CR or PR during the treatment period (or observation phase). The evaluation period for relapse is till the end of the treatment period (or observation phase) in case a (next) treatment period starts, or else till the end of the study. Only the first relapse in a treatment period (or observation phase) will be considered.

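### SAP 4.1.2 items 5 to 7 depart from the amendment 2 endpoint population: earlier entrants who never stopped efgartigimod stay in the off-drug denominator, and no later entrant can have a duration of sustained remission

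*SAP*

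**What the plan says.** Footnote b appears in protocol Table 4 and again in SAP Table 1. It is attached to the two endpoints that require a participant to be off both OCS and efgartigimod: "The endpoint applies only to participants who have stopped receiving efgartigimod PH20 SC before protocol amendment 2 is effective". The protocol's Definitions of Terms give *stop* a specific meaning: ceasing efgartigimod once CR or PR off concurrent BP therapy has lasted 8 weeks or more, possible only before amendment 2. Ceasing for other reasons is a *discontinuation*.

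SAP 4.1.2 derives these two endpoints as items 5 and 6, "for each treatment period separately and additionally for the observation phase". It makes two exclusions. The first covers anyone entering "under protocol version 3 (26 April 2024) or 4 (02 May 2024) will be considered non-evaluable for this endpoint". The second covers participants from the ARGX-113-2009 placebo arm "who enter the ARGX-113-2010 study in the observation phase, will be considered non-evaluable for this endpoint in the observation phase". Everyone else is evaluable, and whoever does not meet the criteria is a non-responder. Under SAP 4.1.3 the number evaluable at least once is the denominator; the off-drug tables follow that pattern in the ROL set.

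Item 7 takes its population from item 5: "Duration of sustained remission will be calculated for participants achieving CR while off both OCS and efgartigimod PH20 SC" for 8 weeks or more, within a treatment period. Its clock starts 7 days after the last IMP dose.

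The protocol's Definitions of Terms contain two versions of sustained remission. Participants ongoing at amendment 2 must be off both concurrent BP therapy and efgartigimod. Those rolling over afterwards need only be off concurrent BP therapy. Duration of sustained remission carries no footnote b. Protocol 4.2, however, still describes the aim as sustained remission once efgartigimod has been stopped.

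**The concern.** The SAP repeats footnote b in its own endpoint table and then applies a different test. Entry version stands in for having stopped, and the two differ for version 1 or 2 entrants who stayed on drug. Protocol 6.3.2, Situations 4A and 4B, keeps those still receiving efgartigimod at amendment 2 on it. The off-drug proportions would then describe a mixed group in which some members had no opportunity to respond.

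Item 7 inherits the entry-version rule. A protocol-defined group, the post-amendment rollovers, has a definition of sustained remission but no derivation. A reader of the resulting table could take it as covering the study, when it can contain only version 1 or 2 entrants.

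**Working it through.** The plan gives no sample size, count or rate for these endpoints, so there is no figure to reproduce. The check sets the rules side by side, counts days, and illustrates the dilution.

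**Step 1: rules by type of entrant**

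| Entrant | Footnote b applies | Evaluable under items 5–6 | Protocol definition of sustained remission | Item 7 can give a duration |
|---|---|---|---|---|
| v1/v2, stopped before amendment 2 | yes | yes | off-drug version | yes |
| v1/v2, never stopped | no | yes | off-drug version, not reachable while on drug | no, if only treatment-period days count |
| v3/v4 | no | no | version without off-drug condition | no |

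The mismatches are row 2 (items 5–6) and row 3 (item 7).

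**Step 2: off-drug days for a participant dosed weekly to week 48**

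Inputs: dosing may run to week 48 (protocol Table 2, footnote l); the week 48 window is ±7 days (same table); SAP Table 2 ends the treatment period at "Date of week 48 or EDV visit"; item 5 needs 56 days.

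- Last dose at the visit: 0 days.
- Last dose one week earlier: 7 days; with the visit at the end of its window, 7 + 7 = 14.
- Shortfall: 56 − 14 = 42 to 56 − 0 = 56 days.

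A never-stopper who discontinues early is in a similar position: the EDV is planned within 7 days of the final dose (protocol 7.1.1) and ends the treatment period.

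**Step 3: do follow-up days count?**

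Follow-up is a separate phase beginning at "End of previous phase + 1 minute" (SAP Table 2). The heading above item 5 names treatment periods and the observation phase only. Item 8, by contrast, runs to the end of the treatment period "in case a (next) treatment period starts, or else till the end of the study". The natural reading is that follow-up days do not count.

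If they did, the last visit falls at 56 ± 3, so 53 to 59 days after the week 48 visit. Off-drug days would be 0 + 53 = 53 to 14 + 59 = 73, a margin of −3 to +17 around 56. For someone dosed at the week 48 visit, 4 of the 7 allowed days (56 to 59) would qualify.

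**Step 4: dilution, treatment-period days only**

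Let p be the proportion among those who stopped before amendment 2, and f the share of evaluable participants who never did. Then reported proportion ≈ p × (1 − f). Neither value is in the documents. With p assumed at 60%:

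- f = 0.25: 0.60 × 0.75 = 45%
- f = 0.50: 0.60 × 0.50 = 30%
- f = 0.75: 0.60 × 0.25 = 15%

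The relation is approximate. A never-stopper could still respond after a long temporary interruption, or in the observation phase after discontinuing IMP in the efgartigimod arm of ARGX-113-2009.

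**Step 5: item 7**

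Version 3 or 4 entry means non-evaluable for CROff without IMP, hence not a responder, hence no duration. The number of such entrants who can contribute is 0, with no assumption needed. A start date tied to the last dose also does not fit someone still on drug.

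**The case against.** Four arguments favour leaving the text alone.

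- **Entry version is a workable proxy.** It agrees with footnote b for version 3 or 4 entrants, but not for version 1 or 2 entrants who never stopped.
- **All version 1 or 2 entrants is a sensible denominator.** In-study stoppers had, by definition, already reached CR or PR, so the strict denominator measures maintenance. That is fair, and the interpretation needs a footnote. But the wider denominator answers a question other than the one both documents state, and the SAP does not declare the switch.
- **Protocol 4.2 supports an off-drug meaning of sustained remission.** This stands: the protocol pulls both ways. It calls for reconciliation, and SAP 6.1 as supplied records no choice.
- **Little depends on it.** Also largely true. The number evaluable is tabulated, and disease status, derived responses, IMP dates and durations are listed by participant, so a careful reader could rebuild the figures.

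Three stronger readings go beyond the documents. A reader might infer that everyone on drug at week 48 is a built-in non-responder. That fails: a participant can stop, respond, restart in treatment period 2, and still count because the tables report achievement at least once. A reader might infer that prevention of relapse goes unanalysed in later entrants. It does not: items 8 and 9 cover them. A reader might infer that item 7 ignores other BP treatment. The start of OCS or rescue therapy already ends the duration; only TCS given for BP and not flagged as rescue is missed.

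**Conclusion.** Both mismatches hold on the text. Items 5 and 6 admit participants whom footnote b excludes. On the natural reading, those dosed continuously to week 48 cannot respond, so the reported proportions are pulled down. Item 7 cannot produce a duration for any post-amendment entrant, although the protocol defines the state for them.

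The direction of the first effect rests on follow-up days being excluded; if they count, never-stoppers could also enter the numerator and the direction is unknown. Its size cannot be derived, and the percentages shown are illustrations on assumed p and f. The second effect rests on no assumed number, but whether the protocol intends an on-drug duration depends on settling the Definitions of Terms against protocol 4.2. This should be fixed before the tables are produced.

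**What to change.** **Items 5 and 6.**
- Make evaluable only participants who stopped efgartigimod before amendment 2 was effective, flagged from IMP dates, disease-status episodes and the amendment's effective date.
- In the observation phase, apply the same test to efgartigimod-arm entrants: state whether a stop in ARGX-113-2009 counts, and do not treat those who discontinued IMP and needed rescue as having stopped. Keep the placebo-arm exclusion.
- Show the number non-evaluable.
- Confirm that follow-up days do not count toward the 56, or state that they do.
- Footnote that, for in-study stoppers, the result is maintenance of response among participants already in CR or PR off concurrent BP therapy.

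**Item 7.**
- Keep the off-drug derivation for all version 1 or 2 entrants, including those who left or completed before the amendment took effect.
- Add a separate, unpooled row for post-amendment rollovers using the protocol definition: BPDAI activity 0 and no pruritus, transient lesions tolerated (or state that reported CR is used instead), while off concurrent BP therapy for at least 56 days. The protocol already counts TCS as concurrent BP therapy.
- Start on the first day of that run, but not before study baseline. Report participants already in remission at baseline separately.
- End at the first of relapse or start of any concurrent BP therapy; censor at end of study.
- Reconcile the Definitions of Terms with protocol 4.2, or record in SAP 6.1 which definition each row uses.

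**Cost.** SAP wording, one revised flag, one table row, and one added input: the effective date of amendment 2 by site or participant. The other inputs are already collected. The price is smaller denominators for the off-drug proportions.

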gMG	generalized myasthenia gravis
GTI	Glucocorticoid Toxicity Index
GTI-AIS	GTI Aggregate Improvement Score
GTI-CWS	GTI Cumulative Worsening Score
GTI-SL	GTI Specific List
HGRAC	Human Genetic Resources Administration of China

Abbreviation	Expansion
IB	Investigator's Brochure
ICF	informed consent form
ICH	International Council for Harmonisation of Technical Requirements for Pharmaceuticals for Human Use
IEC/IRB	independent ethics committee/institutional review board
IGA-BP	Investigator Global Assessment of Bullous Pemphigoid
IgG	immunoglobulin γ
IMP	investigational medicinal product
ITP	immune thrombocytopenia
IV	intravenous(ly)
MedDRA	Medical Dictionary for Regulatory Activities
NCI	National Cancer Institute
NRS	numerical rating scale
OCS	oral corticosteroids
OLE	open-label extension
PD	pharmacodynamic(s)
PR	partial remission
PRO	participant-reported outcome
PT	Preferred Term
QoL	quality of life
QTL	quality tolerance limit
rHuPH20	recombinant human hyaluronidase PH20
SAE	serious adverse event
SAP	statistical analysis plan
SC	subcutaneous(ly)
SoA	schedule of activities
SOC	System Organ Class
SUSAR	suspected unexpected serious adverse reaction
TCS	topical corticosteroids
ULN	upper limit of normal
WOCBP	women of childbearing potential

Definitions of Terms

- Efgartigimod PH20 SC Efgartigimod for SC administration coformulated with rHuPH20
- Concurrent BP therapy Therapy administered in this study for the treatment of BP other than efgartigimod PH20 SC. This may include:
 - Rescue therapy administered in ARGX-113-2009
 - OCS
 - TCS
- Stop of efgartigimod PH20 SC Occurs when the participant stops receiving efgartigimod PH20 SC after achieving CR or PR off concurrent BP therapy for ≥ 8 weeks.
Only applicable before protocol amendment 2 was effective.
- Discontinuation of efgartigimod PH20 SC Occurs when the participant stops receiving efgartigimod PH20 SC before the end of the study for reasons other than achieving CR or PR off concurrent BP therapy for ≥ 8 weeks (refer to Section 7.1)

The following definitions are based on consensus definitions (Murrell et al, 2012¹) and will be applied in ARGX-113-2010:

- Control of disease activity (CDA) The point at which new lesions cease to form and established lesions begin to heal, and pruritic symptoms start to abate
- Treatment failure The absence of CDA despite receiving efgartigimod PH20 SC with escalated dosages of prednisone (or equivalent OCS)

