Escalated dosages of OCS are defined as prednisone (or equivalent OCS) 0.5 mg/kg/day for 1 to 3 weeks, followed by 0.75 mg/kg/day for ≤ 3 weeks, and 0.75 or 1.0 mg/kg/day for a final optional week.
- Transient lesions New lesions that heal within 1 week or pruritus lasting < 1 week
- Nontransient lesions New lesions that do not heal within 1 week or pruritus continuing > 1 week
- Minimal OCS therapy An oral prednisone (or equivalent OCS) dosage of ≤ 0.10 mg/kg/day
Note: For the purpose of this protocol, “oral prednisone” refers to doses/dosages of prednisone or an alternative, equivalent OCS (eg, prednisolone).
- Complete remission (CR) The absence of new lesions, complete healing of existing lesions, and absence of pruritus (except postinflammatory changes, including hypo/hyper pigmentation or skin damage)
- Partial remission (PR) The presence of only new transient lesions

- Sustained remission
 - For participants ongoing in the study when protocol amendment 2 is effective:
 - Healing of lesions with no nontransient lesions (ie, BPDAI activity score of 0) and absence of pruritus while the participant has been off both concurrent BP therapy and off efgartigimod PH20 SC for ≥ 8 weeks
 - New lesions that heal within 1 week or pruritus lasting < 1 week and clearing without treatment will not be considered to change the condition of sustained remission.
 - For participants rolling over after protocol amendment 2 is effective:
 - Healing of lesions with no nontransient lesions (ie, BPDAI activity score of 0) and absence of pruritus while the participant has been off concurrent BP therapy for ≥ 8 weeks.
 - New lesions that heal within 1 week or pruritus lasting < 1 week and clearing without treatment will not be considered to change the condition of sustained remission.
- Relapse
 - Appearance of 3 or more new lesions/month (blisters, eczematous lesions, or urticarial plaques) or at least 1 large (> 10 cm diameter) eczematous lesion or urticarial plaque that does not heal within 1 week, or extension of established lesions or daily pruritus in a participant who has achieved CDA.

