6.3. Assignment to Study Intervention

The following general principles apply to all participants. These principles apply to the specific situations described in Section 6.3.1 and Section 6.3.2 unless mentioned otherwise.

- Efgartigimod PH20 SC can be initiated until week 45 to ensure a minimum of 4 weeks of treatment.
- Efgartigimod PH20 SC should be initiated without concurrent OCS if the participant's BP disease status permits it, according to the investigator's clinical judgment.
- Localized lesions should be treated with TCS before concurrent OCS treatment is considered, if possible.
- If there is no improvement in the participant's BP disease status and additional BP therapy is required while receiving efgartigimod PH20 SC, concurrent OCS treatment may be initiated according to the investigator's clinical judgment. Recommendations for OCS therapy initiation and tapering are provided in Section 6.9.1.
- As described in Section 6.9.2, rescue therapy will be tapered or discontinued in participants who received it in ARGX-113-2009. IMP will be permanently discontinued if the investigator considers it not to be in the participant's best interest to taper or discontinue rescue therapy.

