1.3 STATISTICAL HYPOTHESIS

No formal hypothesis testing will be conducted in this open-label study.

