3.3.2 Derivation rules

Based on their start and stop dates, therapies and procedures will be allocated to each phase, period and subperiod during which the participant received the therapy.

Therapies/procedures with (partially) missing dates will be allocated to each possible phase/(sub)period unless the available parts of the therapy/procedure start or stop date provide evidence not to do so.

Concomitant therapies/procedures are therapies/procedures for which the available information indicates that the therapy/procedure is taken/performed on or after study day 1. In case of doubt (e.g. partially missing dates), it will be assumed that the therapy/procedure is concomitant.

OCS therapy is defined as any record from any eCRF page with medication class = 'GLUCOCORTICOIDS' and route = 'ORAL'.

TCS therapy is defined as any record from any eCRF page where medication class contains 'CORTICOSTEROIDS' and route = 'TOPICAL'.

Rescue therapy is defined as any therapy that is indicated as rescue therapy by the investigator on the eCRF page.

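### SAP item 7 lets sustained remission run on after topical steroids for BP, or after lesions or pruritus short of relapse, which the protocol's definition does not allow

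*SAP*

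**What the plan says.** **SAP 4.1.2, item 7:** "Duration of sustained remission will be calculated for participants achieving CR while off both OCS and efgartigimod PH20 SC for ≥ 8 weeks". These are the item 5 responders: 56 days simultaneously in reported CR, off OCS, off IMP and without flagged rescue therapy. The clock starts 7 days after the last IMP dose. It stops at the first of relapse, a next treatment period, OCS start or rescue start. If none occurs, the participant is censored at the end of the last phase. Table 14.2.1.6 gives the Kaplan-Meier results.

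**Protocol, Definitions of Terms, sustained remission (participants ongoing when amendment 2 took effect):** lesions healed with none that are nontransient (a BPDAI activity score of zero is the stated gloss). The definition further requires "absence of pruritus while the participant has been off both concurrent BP therapy and off efgartigimod PH20 SC for ≥ 8 weeks". One tolerance is given: "New lesions that heal within 1 week or pruritus lasting < 1 week and clearing without treatment will not be considered" to alter that state.

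**Protocol, Definitions of Terms, concurrent BP therapy:** "Therapy administered in this study for the treatment of BP other than efgartigimod PH20 SC. This may include" three separately listed entries, namely rescue therapy from ARGX-113-2009, OCS and TCS.

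**Protocol 6.3, principles for all participants:** "Localized lesions should be treated with TCS before concurrent OCS treatment is considered, if possible".

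**SAP 3.3.2:** "TCS therapy is defined as any record from any eCRF page where medication class contains" the corticosteroid term and the route is topical. Rescue therapy is defined separately, as whatever the investigator flags as rescue.

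**The concern.** The SAP keeps the protocol's endpoint name but applies a looser rule for when remission is lost. Two routes out of protocol-defined remission have no counterpart in item 7: starting ordinary localized TCS for BP, and a return of nontransient lesions or pruritus that does not amount to relapse. Protocol 6.3 places TCS ahead of OCS for localized lesions, so a mild local return treated topically is foreseeable. For participants who had stopped IMP, restarting it short of relapse is at the investigator's discretion (Protocol 6.3.2), so such a return need not trigger any of the four SAP end events.

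At stake is the meaning of Table 14.2.1.6. A reader would take its durations as time in the state that the protocol defines, when part of that time may be spent with lesions or on topical treatment. The SAP gives no reason for the difference, its section 6.1 shows no entry for it, and no sensitivity analysis is planned.

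**Working it through.** The documents give no expected duration, event count or sample size for this endpoint, so there is no figure to reproduce. The check compares the two rules and then applies the SAP's formula to assumed dates.

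**Step 1: the rules side by side**

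| Occurrence after qualifying | Protocol: remission lost? | SAP item 7: duration ends? |
|---|---|---|
| Relapse | Yes | Yes |
| OCS start | Yes | Yes |
| Rescue therapy start | Yes | Yes |
| IMP restarted in a new treatment period | Yes | Yes |
| TCS for BP, flagged as rescue | Yes | Yes |
| TCS for BP, not flagged as rescue | Yes | **No** |
| Nontransient lesions or pruritus below relapse | Yes | **No** |
| Transient lesions or pruritus clearing untreated | No | No |

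The seventh row is possible because relapse needs at least 3 new lesions in a month, one large lesion not healing within a week, extension of established lesions, or daily pruritus. One or two small nontransient lesions meet none of these.

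**Step 2: inputs**

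- Study end: about 56 weeks (SAP 1.2), so day 56 × 7 + 1 = 393.
- Start date: last IMP day + 7 (SAP item 7).
- Duration: end date − start date + 1 (SAP item 7).
- Assumed: last IMP at week 16 (day 113). Two small nontransient lesions appear and are treated with unflagged TCS at week 26 (day 183). No relapse, OCS, rescue therapy or re-treatment follows.

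**Step 3: one case**

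- The first 56 days off IMP end on day 113 + 56 = 169, before day 183, so the participant qualifies.
- Start: 113 + 7 = day 120.
- Protocol-aligned rule: 183 − 120 + 1 = **64 days, event**.
- SAP item 7: 393 − 120 + 1 = **274 days, censored**.
- Ratio: 274 / 64 ≈ 4.3.

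**Step 4: range of assumed dates**

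Remission is lost 1, 28 or 84 days after the first 56 days off IMP. Off-IMP time is counted from the last dose.

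| Last IMP day | Start day | Loss on day | Aligned rule (event) | SAP (censored) | Excess |
|---|---|---|---|---|---|
| 57 | 64 | 114, 141, 197 | 51, 78, 134 days | 330 days | 279, 252, 196 days |
| 113 | 120 | 170, 197, 253 | 51, 78, 134 days | 274 days | 223, 196, 140 days |
| 169 | 176 | 226, 253, 309 | 51, 78, 134 days | 218 days | 167, 140, 84 days |

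**Step 5: direction**

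In these cases an early event becomes a later censoring. That removes a downward step from the Kaplan-Meier curve and enlarges later risk sets, so the curve cannot be lower at any time. Where relapse, OCS, rescue therapy or re-treatment does follow later, the participant's duration still ends in an event, but at a later date.

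**The case against.** The strongest reply is that item 7 already catches most of what matters. Several parts of it stand.

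- **Treated participants.** A reader might infer that treated participants simply stay in remission until study end. They do not: relapse, re-treatment, OCS and rescue therapy each end the duration. TCS also counts when flagged as rescue, and Protocol 6.9.2 lists whole-body TCS as a rescue type.
- **Lesions at entry.** A reader might infer that the SAP ignores lesions altogether. Qualification needs 56 days of reported CR, which by the protocol's definition means no new lesions, healed lesions and no pruritus. A separate BPDAI check at entry would be largely redundant.
- **TCS at entry.** Under protocol v2.0, IMP was stopped only after at least 8 weeks in CR or PR off concurrent BP therapy, which includes TCS. Entrants under v3.0 or v4.0 are non-evaluable for item 5 and so never reach item 7. Exposure at entry is mainly TCS begun in the first 56 days off IMP, or participants off IMP for other reasons.
- **Importance.** The SAP states: "No formal hypothesis testing will be conducted in this open-label study". Time to relapse (Table 14.2.1.8) is a second durability result. TCS use is tabulated by subperiod, and disease status, lesions, BPDAI and censoring reasons are listed, so a reader could trace individual cases.
- **Any TCS as an end event.** The definition in SAP 3.3.2 carries no indication, so using it unrestricted would end remission for topical steroids given for an unrelated condition.

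None of this supplies the missing end events after qualification. Listings allow the effect to be checked but do not correct the table.

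**Conclusion.** The mismatch is real and lies mainly in the end rule. It biases Table 14.2.1.6 towards longer durations and more censoring. On the assumed dates, the excess is 84 to 279 days per affected participant. Those figures assume that none of the four SAP end events occurs before study end.

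A reader might take the ratio of 4.3 as the size of the bias in the table. The documents do not support that: it describes one constructed participant, and the number of people with unflagged TCS or sub-relapse disease after stopping IMP cannot be derived. The conclusion applies to the protocol's definition for participants ongoing at amendment 2, the only group that item 7 can reach. The change should be made because the reported label would otherwise not carry its protocol meaning, but the endpoint is secondary and descriptive.

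**What to change.** Amend SAP 4.1.2 item 7 as follows.

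1. **Entry:** require no TCS for BP during the qualifying 56 days. Use the TCS definition in SAP 3.3.2, restricted to BP by the reason for use that Protocol 6.9 requires to be recorded.
2. **End:** add two events to the existing list, whichever comes first: (a) the first start of TCS for BP after qualifying; (b) the first loss of remission other than transient lesions or pruritus clearing without treatment. Identify (b) from a reported status other than CR or PR, or from nontransient lesions or pruritus in the lesion, BPDAI activity or itch data. Status alone is not enough, because SAP 4.1.1 says investigators report the best status per episode.

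No BPDAI = 0 check at entry is needed, and items 5 and 6 can stay unchanged, since their wording concerns only OCS and efgartigimod.

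The cost is SAP text and programming on data already collected, including a check that the reason for use separates BP from other indications. The downside is somewhat shorter durations and possibly fewer qualifiers.
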